4.17 Laboratory Data

Template: WCT-TP-ST-005-005 Page 18 of 24 Effective Date: 15-Apr-2016 Confidential

Descriptive statistics of the observed values and change from baseline (continuous data) will be presented by Part, Cohort, and treatment cycle for the following laboratory parameters:

- Hematology: complete blood count (CBC) including hemoglobin, hematocrit, white blood cell count with 5-part differential, red blood cell, platelet, and reticulocyte count
- Hemoglobin A1c (HbA1c)
- Coagulation tests (screening only): prothrombin time (PT), partial thromboplastin time (PTT), international normalized ratio (INR), D-dimer, and fibrinogen
- Blood chemistry: alkaline phosphatase, bicarbonate, calcium, phosphorus, magnesium, albumin, glucose, serum creatinine, and insulin
- Liver function tests: aspartate aminotransferase (AST), alanine aminotransferase (ALT), lactate dehydrogenase (LDH), alkaline phosphatase, total and direct bilirubin, uric acid, total protein, and blood urea nitrogen (BUN)
- Electrolytes: sodium, potassium, and chloride
- Lipids: cholesterol, high-density lipoprotein (HDL), low-density lipoprotein (LDL), and triglycerides

Each blood chemistry and liver function test parameter will be classed as below, within, or above normal range, based on ranges supplied by the laboratory used. Shift tables from baseline to the minimum post-baseline value and separately to the maximum post-baseline value will be presented by Part, Cohort, and overall.

The incidence of post-baseline ALT, AST, ALP, and total bilirubin values meeting CTCAE criteria will be summarized by Part, Cohort, and overall. Refer to Appendix 1 of this SAP for CTCAE definitions for these parameters. Additionally, the incidence of participants meeting Hy's law criteria will be summarized. Hy's law criteria are defined as follows:

- ALT ≥5xULN or
- ALP ≥2xULN or
- ALT ≥3xULN and total bilirubin ≥2xULN

For the third criterion which requires both an elevated ALT and elevated total bilirubin value, both lab values must be elevated at the same visit in order to be counted.

Template: WCT-TP-ST-005-005 Page 19 of 24 Effective Date: 15-Apr-2016 Confidential

The following laboratory parameters will be listed only:

- Serum pregnancy test for female patients of childbearing potential, if applicable
- Routine urinalysis: dipstick and microscopy including protein, glucose, and blood; pH, and specific gravity

A listing of all post-baseline clinically significant ALT, AST, ALP, or total bilirubin measurements, defined as measurements meeting ≥CTCAE grade 3 criteria, recorded throughout the treatment period will be presented.

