#### 6.9 Potential Risks

Based on data from oncology and nononcology clinical studies, participants should be monitored for signs and symptoms of hyperglycemia, skin toxicities (rash maculopapular, rash, pruritus, dermatitis, etc.), stomatitis/mucosal inflammation, transaminase (ALT and AST) elevation, and diarrhea. These potential risks are generally consistent with the PI3K/AKT/mTOR pathway inhibitor class. The current safety information for miransertib can be found in the IB.

Also, based on nonclinical data it has been suggested that miransertib may cause a phototoxic reaction in some participants exposed to the drug and sunlight. The amount of miransertib that may be required to cause such reaction is unknown. All participants should be instructed to avoid exposure to sunlight, to use sunscreen to protect exposed areas of the body (eg, forehead, nose, lips, and hands), and to report symptoms that may be associated with phototoxic reaction (eg, redness, pruritus, swelling, blister formation).

There can be other drug-related risks factors that have not yet been reported.

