## 7.1.9 Further Adverse Event and Serious Adverse Event Defining

Wherever possible, a specific disease or syndrome rather than individual associated signs and symptoms should be identified. However, if an observed or reported sign or symptom is not considered a component of a specific disease or syndrome by the investigator, it should be recorded as a separate AE.

Laboratory data are to be collected as stipulated in this protocol. Clinical syndromes associated with laboratory abnormalities are to be recorded as appropriate (eg, diabetes mellitus instead of hyperglycemia).

Scheduled hospitalizations or elective surgical procedures will not be considered as AEs or SAEs. Prolongation of a scheduled hospitalization can be considered an SAE.

Complications associated with scheduled procedures are considered AEs or SAEs.

Treatment-emergent AEs, including SAEs are events with the onset or the worsening of the severity that occurred at or any time after administration of the first dose and through 90 days after the administration of the last dose of the study medication.

Any AEs, including SAEs which are observed before administration of the study medication should be reported as medical history.

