#### 9.4 Safety Analysis

All participants who receive at least one dose of study treatment will be evaluated for safety. The incidence rates of TEAEs, treatment-related adverse events, and serious adverse events (SAEs will be described, as identified with preferred terms and MedDRA system organ class.

The frequency of occurrence of overall toxicity, categorized by the maximum toxicity grades (severity), will also be described. Listings of laboratory test results and CTCAE grades will be generated, and descriptive statistics summarizing the changes in laboratory tests over time will be presented.

The safety analyses will be presented by dose and overall using the Safety Population. Safety assessments include AEs, 12-lead ECGs, physical examination, clinical laboratory, and home fasting glucose measurements.

Adverse events will be graded according to the current version of CTCAE.

Exploratory analyses will also be performed on other safety parameters, as deemed appropriate, and within subgroups defined by age, sex, race, mutation status, prior therapies, medical history, and other prognostic factors. Exploratory analyses may also be performed on previously collected laboratory analytes, including PK samples.

Exposure to study treatment over time will be summarized with time on treatment, total amount of administered treatment, dose intensity and relative dose intensity.

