9 APPENDIX 1: CTCAE GRADES FOR SELECT LABORATORY PARAMETERS

Parameter	Unit	Definition	Grade 1	Grade 2	Grade 3	Grade 4
ALT	U/L	High	>ULN-3.0xULN if baseline was normal; 1.5-3.0x baseline if baseline was abnormal	baseline was normal; >3.0-5.0x baseline if	baseline was	>20.0xULN if baseline was normal; >20.0x baseline if baseline was abnormal
AST	U/L	High	baseline was normal;	>3.0-5.0x baseline if	baseline was	>20.0xULN if baseline was normal; >20.0x baseline if baseline was abnormal
Alkaline phosphatase	U/L	High	>ULN-2.5xULN if baseline was normal; 2.0-2.5x baseline if baseline was abnormal	baseline was normal; >2.5-5.0x baseline if	baseline was	>20.0xULN if baseline was normal; >20.0x baseline if baseline was abnormal
Total bilirubin	mg/dL	High		>1.5-3.0xULN if baseline was normal; >1.5-3.0x baseline if	baseline was	>10.0xULN if baseline was normal; >10.0x baseline if baseline was abnormal

Template: WCT-TP-ST-005-005 Effective Date: 15-Apr-2016 Page 23 of 24 Confidential

Issue Date: 09May2022

Parameter	Unit	Definition	Grade 1		Grade 2		Grade 3	Grade 4
			baseline v abnormal	was	baseline abnormal	was	baseline if baseline was abnormal	

ULN=Upper limit of normal

Values in table are based on CTCAE v5.0.

Template: WCT-TP-ST-005-005

Effective Date: 15-Apr-2016

Page 24 of 24

Confidential

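### SAP 4.17 grades only four liver tests and the SAP omits home glucose, both undeclared, so laboratory glucose elevations not reported as hyperglycemia AEs get no threshold or severity summary

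*SAP*

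**What the plan says.** **Protocol.** Section 9.4 states "Listings of laboratory test results and CTCAE grades will be generated" and does not restrict this to particular tests. Its list of safety assessments ends with "clinical laboratory, and home fasting glucose measurements". Section 6.9 says "participants should be monitored for signs and symptoms of hyperglycemia", the first of several risks named there. Section 6.5 gives drug-related hyperglycemia its own table of actions by CTCAE grade (Table 7), while all other drug-related toxicity shares Table 6. Section 7.1.9 adds, on AE recording: "Clinical syndromes associated with laboratory abnormalities are to be recorded as appropriate (eg, diabetes mellitus instead of hyperglycemia".

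**SAP.** Section 4.17 states "The incidence of post-baseline ALT, AST, ALP, and total bilirubin values meeting CTCAE criteria will be summarized by Part, Cohort, and overall", and it closes with "A listing of all post-baseline clinically significant ALT, AST, ALP, or total bilirubin measurements, defined as measurements meeting ≥CTCAE grade 3 criteria". The appendix headed "9 APPENDIX 1: CTCAE GRADES FOR SELECT LABORATORY PARAMETERS" has rows for the same four tests and none for glucose. Glucose does appear in the panel that receives descriptive statistics: "Blood chemistry: alkaline phosphatase, bicarbonate, calcium, phosphorus, magnesium, albumin, glucose, serum creatinine, and insulin". Chemistry and liver parameters also get shift tables in three classes (below, within or above normal), from baseline to the post-baseline minimum and maximum. Section 4.3.7 restricts tabulation to scheduled post-baseline values and sends unscheduled ones to listings. Section 4.15 lists the safety assessments without home glucose, and no other section mentions it. Apart from the general Amendment 7 change of objective, section 7 declares one specific change, the compliance formula.

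**The concern.** After Amendment 7, safety and tolerability is the study's only objective. The protocol manages hyperglycemia separately and by grade, yet the SAP applies laboratory grading to liver tests only. A reader of the study report could learn how many participants reached each grade of ALT, but could not learn from any table how many reached a given glucose level.

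The second issue is traceability. The SAP does less than protocol 9.4 plans on two counts, graded laboratory listings and home glucose, and the section meant to record such differences is silent on both. A later reader cannot tell a decision from an oversight.

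**Working it through.** No sample size or power figure is involved. The check sets the planned outputs side by side and recomputes one table of earlier data.

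**1. Protocol against SAP**

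| Item | Protocol | SAP | Declared in SAP section 7? |
|---|---|---|---|
| CTCAE grades for laboratory results | 9.4: listings with grades, no restriction by test | 4.17 and Appendix 1: ALT, AST, ALP, total bilirubin | No |
| Home fasting glucose | 9.4: named as a safety assessment | Not mentioned | No |
| Severity of hyperglycemia reported as an AE | 7.6: CTCAE grade | 4.16: TEAEs by maximum toxicity, and by grade <3 and ≥3 | Not needed; covered |

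**2. Count of parameters.** The SAP 4.17 chemistry list has 9 entries and the liver list has 9. Alkaline phosphatase is in both, so 9 + 9 − 1 = 17 distinct parameters get the three-class shift. Four of them are also graded, which leaves 17 − 4 = 13 without grades. Glucose is one of the 13.

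**3. What the glucose outputs can show**
- *Shift table.* The screening exclusion is fasting glucose of 160 mg/dL or more above 12 years of age, and 180 mg/dL or more at 12 years or younger (protocol 3.2, and Annex 1 for Part A). A participant over 12 can therefore enter just under 160 mg/dL. The documents give no laboratory normal range. If the local upper limit lies below that entry value (an assumption), the participant is already above normal at baseline. A later value of 160 mg/dL and one of 2 × 160 = 320 mg/dL both read as above to above.
- *By-cycle statistics.* SAP 4.4 includes the minimum and maximum, so an extreme scheduled value would be visible. The tables do not show how many participants passed any level.
- *Unscheduled samples.* Protocol 5.3 allows extra tests between visits to assess an AE. Under SAP 4.3.7 those values enter neither table.
- *Fasting status.* Protocol 5.3 has samples taken after eating in error recorded as fed on the eCRF. SAP 4.17 does not say how such samples are handled.

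**4. Earlier data (protocol Table 1, drug-related hyperglycaemia, adult oncology).** The printed figures reproduce: 1/7 = 14.3% at 60 mg qd, 4/7 = 57.1% at 80 mg qd, 5/28 = 17.9% in total. Blank cells count as zero, which agrees with the total (1 + 4 = 5).
- At 40 mg or less: n = 4 + 3 + 3 + 4 = 14, so 0/14. The two-sided exact 95% upper limit is 1 − 0.025^(1/14) ≈ 23%.
- At 60 mg or less: n = 14 + 7 = 21, so 1/21 = 4.8%.

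Protocol 1.3.1.1 puts the MTD at 60 mg qd, about 30 mg/m². The planned Part B dose level is at most 25 mg/m².

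**The case against.** The strongest reply is that severity of hyperglycemia is already reported. A reader might infer that the SAP gives it no severity summary at all, and the documents do not support that. Protocol 7.1.1 allows an abnormal laboratory finding to be an AE, Table 7 requires drug-related hyperglycemia to be graded before it can be acted on, and SAP 4.16 tabulates and lists the resulting events, including those that lead to interruption or discontinuation. This stands, and it limits the point to values outside that route.

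Three other strong readings also fail:
- *Section 7.1.9 removes hyperglycemia from the AE data.* The section applies only as appropriate and gives one example. A renamed event is still graded and still tabulated under its new term. The rule weakens capture under the hyperglycemia term but does not abolish it.
- *The severity endpoint covers laboratory values.* Protocol 2.3 and SAP 2.2.1 define it as frequency, duration and severity of AEs.
- *The 57.1% indicates what to expect here.* It comes from seven adults at a dose above the MTD. At 60 mg or less the figure is 1/21. The upper limit of about 23% on 0/14 equally means that the lower doses do not exclude a material rate.

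Two practical objections also stand. Protocol 9.4 plans graded listings, not a glucose incidence table, so such a table goes beyond the protocol's minimum. Home readings are mainly as needed (protocol 5.7), and no section shows that they are entered on the eCRF.

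**Conclusion.** The point holds in a limited form. SAP 4.17 and Appendix 1 narrow protocol 9.4 to four liver tests, home glucose is omitted from the SAP, and section 7 records neither. The practical loss concerns laboratory glucose elevations that are not reported as AEs or are reported under another term. For these, the only categorical output is a three-class shift built from scheduled values, and it cannot show worsening in a participant who starts above normal.

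The number of participants affected cannot be derived from the documents. It depends on how completely sites report glucose elevations as AEs and on local normal ranges, neither of which is given. The earlier oncology data show that the event occurs (0/14, 1/7 and 4/7 with rising dose) but do not set an expected rate for this population.

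**What to change.** 1. In SAP 4.17 and Appendix 1, add the incidence of post-baseline fasting glucose at or above stated numeric cut-offs, by Part, Cohort and overall. At minimum use the protocol's screening values, 160 mg/dL above 12 years and 180 mg/dL at 12 years or younger. Call them reporting thresholds, since one value per age group is not a severity grade.
2. Count scheduled and unscheduled values, as an exception to SAP 4.3.7, and exclude or flag samples recorded as fed.
3. State whether age at baseline or at sampling applies. Treatment may last 48 × 28 = 1,344 days, about 3.7 years, so a child can cross the age limit.
4. Flag values at or above the cut-offs in the laboratory listing.
5. List home glucose values if they are in the database. If they are not, say in SAP section 7 that they are not analysed.
6. Record the narrowing of protocol 9.4 in SAP section 7. This is needed even if the sponsor declines the table.

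The cut-offs are for reporting only and change no dose or clinical rule. The cost is a few table rows and flags from laboratory data already collected. As-needed home readings can be listed but cannot support an incidence.

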ARQ 092 in Children and Adults with Proteus Syndrome"; NCT02594215). The primary endpoint of the study was to determine the biological effect of miransertib measured by changes of phosphorylated AKT (pAKT) levels in the affected tissue. Secondary endpoints included safety, tolerability, and disease specific evaluations (volumetric magnetic resonance imaging [MRI], photography of the cerebriform connective tissue nevus [CCTN], quality of life [QoL], and functional assessments). The study initially enrolled 3 adult patients. Once miransertib was shown to be well tolerated, additional 3 younger patients (<18 years of age) were enrolled. All participants were treated at a daily dose of 5 mg/m^2 and were expected to complete 12 cycles of treatment, with a cycle being defined as a 28-day period. Of the 6 enrolled participants, 2 discontinued treatment after 8 cycles (due to withdrawal of consent and an adverse event of transaminase increase), 3 participants completed 12 cycles, and 1 participant continues treatment after completion of 12 cycles. In 5 participants, a reduction of 50% or greater of tissue pAKT levels was reported, and the primary endpoint of the study was met. The clinical efficacy measurements showed reduction in size of the CCTN at Cycle 12 by quantitative standardized photography. The 3 younger participants reported an improvement in pain as assessed by a standardized pain scale. The drug was well tolerated with most adverse events (AEs) being mild to moderate in severity.

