In Cohort 5, 80 mg qd, one of the first 3 participants experienced 2 DLTs (Grade 3 cardiac failure congestive and Grade 4 cardiomyopathy) and the Cohort was expanded to enroll 3 additional participants. After 2 more DLTs (Grade 3 maculopapular rash and Grade 3 hyperglycemia) were experienced by 2 other participants, qd dosing was reduced to 60 mg for Cohort 6. In Cohort 6, one of the first 3 participants experienced a DLT (Grade 3 increased AST) and the Cohort was expanded with no additional DLTs reported. The MTD was declared as 60 mg qd for the continuous dosing schedule.

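### SAP 4.17 counts isolated ALT or ALP rises as Hy's law and leaves AST out of the paired criterion

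*SAP*

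**What the plan says.** SAP 4.17 announces a participant-level count: "the incidence of participants meeting Hy's law criteria will be summarized. Hy's law criteria are defined as follows". Three bullets follow, joined by or:

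1. ALT at or above 5×ULN.
2. ALP at or above 2×ULN.
3. "ALT ≥3xULN and total bilirubin ≥2xULN".

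The next sentence requires both values at one visit, for the third criterion only, so the first two stand alone and need no bilirubin value. The SAP does not say whether the three are shown on separate rows or pooled.

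The other liver outputs in 4.17 take one analyte at a time: CTCAE incidence for ALT, AST, ALP and total bilirubin; shift tables; and a listing of clinically significant values, "defined as measurements meeting ≥CTCAE grade 3 criteria". Appendix 1 gives the grades, which depend on whether baseline was normal. Grade 1 for ALP is ">ULN-2.5xULN if baseline was normal; 2.0-2.5x baseline if baseline was abnormal"; for ALT it is ">ULN-3.0xULN if baseline was normal; 1.5-3.0x baseline if baseline was abnormal".

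Protocol 6.9 names "transaminase (ALT and AST) elevation, and diarrhea" among the risks to monitor.

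**The concern.** A count headed Hy's law will be read as participants with a transaminase rise together with a bilirubin rise. As defined, it fails in both directions.

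- **It counts too much.** An ALT or ALP value alone qualifies, whatever the bilirubin. Some qualifying ALP values are Grade 1 or ungraded in the SAP's own appendix, while the same section sets clinical significance at Grade 3. The hepatic entry limits (Protocol 3.1.1, and Annex 1 for Part A) cover bilirubin, AST and ALT but not ALP, so a participant can enter above the ALP threshold.
- **It counts too little.** AST is in no criterion, although the protocol names both transaminases as a risk and reports a Grade 3 AST increase as a dose-limiting toxicity in the oncology study (Protocol 1.3.1.1). In the earlier Proteus study, two of six participants stopped treatment early, "due to withdrawal of consent and an adverse event of transaminase increase".

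Safety and tolerability is the sole objective (Protocol 2.1, SAP 2.1.1), and this is the only planned summary that pairs a transaminase with bilirubin. SAP section 6 sends a subset of the outputs to the DMC without saying whether this table is among them.

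**Working it through.** There is no stated figure to reproduce. The check applies the SAP rule literally and compares it with a paired rule that admits either transaminase. All values are multiples of ULN.

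- SAP rule: ALT ≥5, or ALP ≥2, or (ALT ≥3 and bilirubin ≥2).
- Paired rule: (ALT ≥3 or AST ≥3) and bilirubin ≥2.

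**Threshold patterns.** ALT has three levels (<3, 3 to <5, ≥5); AST (<3, ≥3), ALP (<2, ≥2) and bilirubin (<2, ≥2) have two each: 3 × 2 × 2 × 2 = 24 patterns.

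- SAP rule: 12 patterns with ALP ≥2; with ALP <2, 4 more with ALT ≥5 and 2 more with ALT 3 to <5 and bilirubin ≥2. Total 12 + 4 + 2 = 18.
- Paired rule: 12 patterns with bilirubin ≥2, less the 2 in which both transaminases are <3. Total 10.
- Flagged by both: 9. SAP rule only: 18 − 9 = 9. Paired rule only: 10 − 9 = 1. Neither: 24 − 9 − 9 − 1 = 5.

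Eight of the nine SAP-only patterns have bilirubin <2; the ninth has bilirubin ≥2 and ALP ≥2 with neither transaminase at 3. The one missed pattern is AST ≥3, bilirubin ≥2, ALT <3, ALP <2. If ALP is ≥2, the participant is counted, but through the ALP criterion.

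**Worked cases against Appendix 1.**

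| Case (×ULN) | Appendix 1 grade | SAP rule | Paired rule |
|---|---|---|---|
| ALP 2.0 to 2.5, normal baseline, others normal | Grade 1 (up to 2.5×ULN) | counted | no |
| ALP 1.2 → 2.0, others normal | 2.0/1.2 = 1.67× baseline, below the 2.0× floor: none | counted | no |
| ALP 2.2 throughout, others normal | 2.2/2.2 = 1.0× baseline: none | counted | no |
| ALT 3.5, bilirubin 2.2 | not needed | counted | counted |
| AST 1.5 → 6, bilirubin 2.5 and ALT 2.5 (both from normal), ALP normal | AST 6/1.5 = 4.0× baseline, Grade 2; bilirubin Grade 2; ALT Grade 1 | missed | counted |

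The last case also stays out of the Grade 3 listing, because nothing in it exceeds Grade 2.

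**Why the fixed-ULN rows still have a use.** Entry allows ALT up to 3×ULN. From that baseline, Grade 1 runs to 3 × 3.0 = 9×ULN and Grade 2 to 3 × 5.0 = 15×ULN, so the Grade 3 listing starts only above 15×ULN. From 2×ULN, a rise to 5.5×ULN is 5.5/2 = 2.75× baseline, still Grade 1. Fixed multiples of ULN therefore show rises that baseline-relative grades do not.

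**Illustration with assumed rates.** The documents give none. If a proportion p of about 65 Part B participants had an isolated ALT ≥5 or ALP ≥2, the expected number counted is 65p and the chance of at least one is 1 − (1 − p)^65.

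| Assumed p | Expected number | Chance of at least one |
|---|---|---|
| 1% | 0.65 | 48% |
| 5% | 3.25 | 96% |
| 10% | 6.5 | 99.9% |

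**The case against.** The SAP discloses its definition in full, and the protocol gives no competing one, so the documents do not contradict each other. The conventional meaning of the term comes from outside them. Nothing says the three criteria are pooled; if each has its own row, the ALT-plus-bilirubin count can be read directly.

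Other outputs also help. Protocol 9.4 plans listings of laboratory results with no Grade 3 floor, and SAP 4.3.7 lists unscheduled and repeat values. The AST example would add a Grade 2 AST and a Grade 2 bilirubin to the CTCAE tables. The missed pattern is one of 24, and at AST 6×ULN it escapes the Grade 3 listing only because baseline AST was abnormal. Neither the oncology AST event nor the Proteus discontinuation is reported with a bilirubin rise. The table is descriptive, and SAP section 4 allows extra tables in the study report.

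Much of this stands: the size is unknown, no test or treatment rule depends on the count, and the cases can be rebuilt by hand. It does not remove the fault. Separate rows would cure neither the label nor the AST gap. The listings sort by participant, then parameter, then cycle (SAP 4.4), so same-visit pairs must be matched manually, and no planned table gives a paired count involving AST. Nor does the argument need an outside definition: the protocol treats both transaminases as the risk, and the SAP includes AST in every other summary of hepatic enzymes in 4.17.

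**Conclusion.** The definition is wrong as written and should be corrected. It puts single-analyte ALT and ALP values under a label that readers will take to mean a transaminase rise with a bilirubin rise, and it omits AST-driven pairs. The definitional size is nine of 24 threshold patterns flagged only by the SAP rule and one flagged only by the paired rule. These are not patient counts, and the number of participants affected cannot be estimated from the documents.

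The conclusion rests on the printed criteria and the Appendix 1 cut-offs, and on reading the Hy's law label as a paired finding. The consequence is a mislabelled descriptive safety count in a study whose only objective is safety. No error rate, power, stopping rule or dose rule is affected.

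**What to change.** In SAP 4.17:

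- Rename the set liver laboratory criteria and report each criterion in its own row. Keep the ALT ≥5×ULN and ALP ≥2×ULN rows, since baseline-relative grades can hide them.
- Report potential Hy's law cases only as post-baseline, same-visit ALT or AST ≥3×ULN with total bilirubin ≥2×ULN.
- Show the concurrent ALP for each such case, for example split at 2×ULN, rather than excluding cases on ALP.

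The cost is one SAP paragraph and one table shell. All four analytes are already in the protocol's liver function panel (Protocol 5.3), so no new data are needed. No change to the scheduled-visit rule in SAP 4.3.7 is proposed here, and no clinical rule is touched.
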